9.4.3 SAFETY ANALYSES

Safety endpoints include:

- Dates and associated diagnoses of emergency department visits within 30 days of discharge
- Discharge opioid prescription refills

The study statistician will regularly analyze these endpoints as outlined in section 8.2.

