1 PROTOCOL SUMMARY

1.1 SYNOPSIS

Title:	Postoperative Nudges to Reduce Opioid Prescribing (POST-OP)
Study Description:	This study tests the effectiveness of two email-based behavioral nudges, one based on peer behavior and one based on best practice guidelines, in reducing excessive opioid prescriptions after surgery. It will be conducted in three surgical specialties (general surgery, orthopedic surgery, and obstetric/gynecological surgery) at 19 hospitals within one healthcare system. At each hospital, these specialties will each be randomized to a control group or one of two nudge groups. Both types of email-based nudges are expected to reduce opioid prescribing after surgery.
Objectives:	Primary Objective: Health Services Research Secondary Objectives: Basic Science
Endpoints:	Primary Endpoint: Share of discharge opioid prescriptions above prescribing guidelines Secondary Endpoints: 
• Morphine milligram equivalents (MMEs) prescribed at discharge• Days' supply of opioids prescribed at discharge• Share of discharges where any opioid was prescribed• Share of patients on opioids for greater than 3 months post-discharge• Number of 30-day all-cause emergency department visits• Number of 30-day all-cause hospitalizations• Share of discharge opioid prescriptions above prescribing guidelines in the year after the intervention ends

Study Population:	Surgeons in northern California
Phase:	N/A
Description of Sites/Facilities Enrolling Participants:	19 Sutter Health hospitals
Description of Study Intervention:	Each month for one year, surgeons in the nudge groups will receive emails comparing their opioid prescribing either to their peers' prescribing or to prescribing guidelines.
Study Duration:	24 months
Participant Duration:	12 months

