3 OBJECTIVES AND ENDPOINTS

OBJECTIVES	ENDPOINTS
Primary	
To test the effectiveness of two behavioral nudges, one based on peer behavior and one based on best practice guidelines, in reducing the share of discharge opioid prescriptions above procedure-specific prescribing guidelines	Share of discharge opioid prescriptions above prescribing guidelines
Secondary	
To test the effectiveness of two behavioral nudges, one based on peer behavior and one based on best practice guidelines, in reducing the morphine milligram equivalent quantities and days' supply prescribed at discharge	Morphine milligram equivalents (MMEs) prescribed at discharge, days' supply of opioids prescribed at discharge
To test the effectiveness of two behavioral nudges, one based on peer behavior and one	Share of discharges where any opioid was prescribed

OBJECTIVES	ENDPOINTS
based on best practice guidelines, in reducing the share of discharges with any opioids prescribed	
To test the long-term effects on patients of two behavioral nudges, one based on peer behavior and one based on best practice guidelines	Share of patients on opioids for greater than 3 months post-discharge
To test the persistence of the effectiveness of two behavioral nudges, one based on peer behavior and one based on best practice guidelines, in reducing the share of discharge opioid prescriptions above procedure-specific prescribing guidelines	Share of discharge opioid prescriptions above prescribing guidelines in the 12 months after the nudges stop being delivered
To test the safety of two behavioral nudges, one based on peer behavior and one based on best practice guidelines	Number of 30-day all-cause emergency department visits, number of 30-day all-cause hospitalizations

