8.2 SAFETY AND OTHER ASSESSMENTS

All safety assessments will be conducted using data collected from the Sutter Health electronic health record. Data collected will include:

- Dates and associated diagnoses of emergency department visits within 30 days of discharge
- Discharge opioid prescription refills

The study statistician will regularly create three reports for each outcome. Each report will feature a set of ratios indicating the relative frequency of adverse events in a different context. The reports will contain the numerator, denominator, and ratio, each individually reported. Reports will be produced at the end of each month of the trial, including through the 1-year post-intervention period. They will be presented and discussed at half-yearly DSMB meetings.

- Report 1: Adverse events per arm
 - a) Numerator: number of adverse events among intervention arm 1 (INT1) patients
 - Denominator: total number of INT1 patients meeting the inclusion criteria

- b) Numerator: number of adverse events among intervention arm 2 (INT2) patients
Denominator: total number of INT2 patients meeting the inclusion criteria
- c) Numerator: number of adverse events among the control patients
Denominator: total number of control patients meeting the inclusion criteria

- Report 2: Adverse events per arm among patients of surgeons who ever received a treatment email
 - a) Numerator: number of adverse events among patients whose surgeon ever received an INT1 email
Denominator: total number of patients whose surgeon ever received an INT1 email
 - b) Numerator: number of adverse events among patients whose surgeon ever received an INT2 email
Denominator: total number of patients whose surgeon ever received an INT2 email

Notes: Ever received an INT1/INT2 email means that the surgeon is included if they received an INT1/INT2 email in any month of the trial. We will also compare the report 2 ratios to the report 1 control ratio (item c above) for additional context.

- Report 3: Adverse events per arm among patients who were prescribed an opioid at discharge and whose surgeon who ever received a treatment email
 - a) Numerator: number of adverse events among patients prescribed opioids at discharge and whose surgeon ever received an INT1 email
Denominator: total number of patients prescribed opioids at discharge and whose surgeon ever received an INT1 email

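### The monthly safety reports do not commit to hospitalisation ratios, and Reports 2 and 3 apply the ever-emailed filter to the nudge arms only (minor)

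*Combined protocol and SAP*

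**What the plan says.** Section 3 ties the safety objective to "Number of 30-day all-cause emergency department visits, number of 30-day all-cause hospitalizations". The Synopsis (1.1) and Section 9.4.2 carry the same two items as secondary endpoints; the Synopsis entry reads "Number of 30-day all-cause hospitalizations". Section 9.4.3 says that the safety endpoints include "Dates and associated diagnoses of emergency department visits within 30 days of discharge" and "Discharge opioid prescription refills", and refers to Section 8.2 for their analysis. Section 8.2 names the same two items as its safety data.

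Section 8.2 then sets out the monitoring: "The study statistician will regularly create three reports for each outcome". On their purpose it says "Each report will feature a set of ratios indicating the relative frequency of adverse events in a different context", and on timing "Reports will be produced at the end of each month of the trial, including through the 1-year post-intervention period". The reports go to half-yearly DSMB meetings.

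Report 1 counts all eligible patients in each arm. Report 2 keeps nudge-arm patients whose surgeon ever received an email, and the plan says its ratios will also be compared with the Report 1 control ratio, as added context. Report 3 restricts every row to patients prescribed an opioid at discharge, and restricts the two nudge rows further to ever-emailed surgeons. The filter is defined thus: "Ever received an INT1/INT2 email means that the surgeon is included if they received an INT1/INT2 email in any month of the trial". Under Section 6.1.1 an email requires at least two of the surgeon's discharges in a month to exceed the guideline.

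**The concern.** There are two separate issues.

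First, a named safety endpoint is absent from the list that feeds the routine safety tables. A statistician following 8.2 as written would produce ED-visit and refill ratios each month and no hospitalisation ratios. Refills, in turn, are called a safety endpoint in 9.4.3 but do not appear in Section 3.

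Second, being emailed is a post-randomisation event that depends on the surgeon's volume and prescribing. Filtering the nudge arms on it but not the control arm gives contrasts that are not like-for-like. Report 3 also conditions on opioid receipt, which is itself a secondary outcome that the nudges may change. The filter has no date limit, so discharges before a surgeon's first email count as well. The DSMB sees these tables and may recommend stopping the intervention (7.1), yet nothing in the text marks the contrasts as non-randomised.

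**Working it through.** The plan gives no safety event rate, trigger rate, surgeon volume or safety power, so there is no stated figure to reproduce. Steps 1 and 2 compare the text. Steps 3 to 5 are illustrations on assumed inputs.

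**Step 1. The lists side by side.**

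| Place | ED visits | Hospitalisations | Refills |
|---|---|---|---|
| 1.1 secondary endpoints | yes | yes | no |
| 3 safety objective | yes | yes | no |
| 9.4.2 secondary outcomes | yes | yes | no |
| 8.1 data collected | yes | yes (inpatient visits) | yes |
| 8.2 safety data | yes | no | yes |
| 9.4.3 safety endpoints | yes | no | yes |

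ED visits are the only item common to Section 3 and Section 9.4.3. Section 8.1 shows that all three are extracted.

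**Step 2. The filters side by side.**

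| Report | Nudge rows | Control figure beside them |
|---|---|---|
| 1 | all eligible patients | all eligible patients |
| 2 | surgeon ever emailed | Report 1 control ratio (all eligible patients) |
| 3 | opioid at discharge and surgeon ever emailed | opioid at discharge |

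**Step 3. How selective the trigger can be.** Assume m eligible discharges a month, each above guideline with probability p, independently. The monthly trigger probability is q = P(Binomial(m, p) ≥ 2), and the chance of ever being emailed over 12 mailings is 1 − (1 − q)^12.

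- m = 5, p = 0.10: q = 1 − 0.9^5 − 5(0.1)(0.9^4) = 0.081, so ever-emailed = 0.64. At p = 0.05 it is 0.24; at p = 0.20 it is 0.97.
- m = 2: 0.03, 0.11 and 0.39 at p = 0.05, 0.10 and 0.20.

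The filter therefore favours surgeons with higher volume and a higher above-guideline share.

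**Step 4. Effect on the Report 2 contrast with no nudge effect.** Let a share f of an arm's patients belong to surgeons who ever trigger, with an event rate r times that of the other patients (rate e). The ever-emailed rate is e·r. The rate over all eligible controls is e(f·r + 1 − f). The ratio is r / (f·r + 1 − f).

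| f | r = 0.8 | r = 1.25 |
|---|---|---|
| 0.5 | 0.8/0.90 = 0.889 | 1.25/1.125 = 1.111 |
| 0.7 | 0.8/0.86 = 0.930 | 1.25/1.175 = 1.064 |
| 0.9 | 0.8/0.82 = 0.976 | 1.25/1.225 = 1.020 |

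The ratio is 1 only if r = 1 or f = 1. It can fall on either side of 1.

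A simulation with no nudge effect agrees. It assumed an event risk near 10%, surgeon above-guideline shares drawn from Beta(1,3), and event odds multiplied by 0.7 to 1.5 per 0.25 increase in that share. For Report 3 it also assumed that 60% of discharges not above guideline carry an opioid.

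| Mean monthly volume | Report 2 ratio | Report 3 ratio |
|---|---|---|
| 2 | 0.905 to 1.112 | 0.907 to 1.107 |
| 5 | 0.948 to 1.059 | 0.949 to 1.055 |
| 10 | 0.969 to 1.033 | 0.970 to 1.031 |

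When event risk was unrelated to prescribing share, every ratio was 1.00.

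**Step 5. With the filter matched.** If the control row is limited to surgeons who would have triggered, both sides have expected rate e·r under no effect, so the ratio is 1 by construction. Report 1 already has this property.

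**The case against.** The best defence of the lists is that they are not closed: 8.2 and 9.4.3 both use wording that permits further items. Hospitalisations are also not lost. Inpatient visits within 30 days are collected (8.1), hospitalisations are analysed by arm as a secondary outcome (9.4.2), and all adverse events go to the next DSMB meeting (8.3.5). The DSMB reviews safety and efficacy data for each arm twice a year and settles its data elements at its organisational meeting (10.1.6). A reader might infer that hospitalisations go unmonitored or are hidden from the DSMB; these provisions do not support that. What stands is narrower: the section that specifies the monthly tables does not commit to them. The adverse-event route is not a full substitute, because 8.3.4 expects events to surface partly while those same reports are prepared, and the seriousness criteria in 8.3.2 do not list hospitalisation as a qualifying outcome.

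On refills, tracking a safety measure that is not also a tested secondary outcome is ordinary practice. Only its relation to Section 3 needs stating.

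On Reports 2 and 3, the denominators are openly described, the Report 2 control comparison is offered only as context, and no test, threshold or stopping rule depends on either report. All of that stands, and it keeps the point minor. It does not make the contrasts like-for-like, and the text does not warn that they are not.

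**Conclusion.** Both parts hold, as a minor point. The text comparison is secure: Section 3 names hospitalisations as a safety endpoint, and the sections governing the monthly reports do not. The filter asymmetry is equally plain in the report definitions.

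The consequence is uncertain. Neither the size nor the direction of any distortion in Reports 2 and 3 can be determined from the documents. The range of 0.89 to 1.11 for Report 2 rests on assumed f and r, and at f = 0.9 it shrinks to 0.98 to 1.02.

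Two stronger readings are tempting and not supported. One is that the safety comparison as a whole is biased: Report 1 keeps every eligible patient by arm and remains a valid randomised comparison. The other is that the Report 3 controls are wholly unselected: they are limited to opioid recipients, as the nudge rows are, and lack only the trigger filter.

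**What to change.** 1. Add 30-day all-cause hospitalisations to 8.2, 9.4.3 and Reports 1 to 3. Reconcile these lists with Section 3, and state that refills are a safety-monitoring measure.
2. In Reports 2 and 3, add a control row limited to control surgeons who would have met the same trigger over the same 12 mailings (October 2021 to September 2022). In every arm, count patients from the surgeon's first actual or would-be email date. A surgeon's first trigger precedes that surgeon's first email, so the rule gives comparable groups unless nudges spill over between colleagues.
3. Label Reports 2 and 3 supplementary and non-randomised, and name Report 1 as the primary safety comparison. Note that Report 3 conditions on opioid receipt, which the matched row does not remove.

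The cost is a small amount of report programming and some wording. The inpatient, refill and prescribing data are already extracted (8.1), and the trigger code exists and has been checked (6.2.4, 10.1.8). If only wording can change, steps 1 and 3 still commit the plan to hospitalisation ratios and remove the risk of misreading.

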 - b) Numerator: number of adverse events among patients prescribed opioids at discharge and whose surgeon ever received a nINT2 email
Denominator: total number of patients prescribed opioids at discharge and whose surgeon ever received an INT2 email
 - c) Numerator: number of adverse events among control patients prescribed opioids at discharge
Denominator: total number of control patients prescribed opioids at discharge

Notes: Ever received an INT1/INT2 email means that the surgeon is included if they received an INT1/INT2 email in any month of the trial.

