10.1.9 DATA HANDLING AND RECORD KEEPING

10.1.9.1 DATA COLLECTION AND MANAGEMENT RESPONSIBILITIES

The following data will be collected by investigators at Sutter Health and the RAND Corporation:

- Interview data. The study team will interview Sutter Health providers about their workflows prior to implementation of the nudges and their experiences of the nudges after implementation. Staff at Sutter Health will facilitate arranging the interviews, so we will not be collecting names and contact information for recruitment.
- Electronic health record (EHR) data. This study will analyze data on clinician prescribing behavior, patient demographic data, and patient clinical data extracted from Sutter Health's EHR. Study team members employed by Sutter Health will extract the data from the EHR, remove all elements of PHI except dates and hospital names, and share this limited dataset within the study team by uploading it to a folder within the project's Teamspace extranet site. Study team members may store this data locally on their password-protected institutionally issued computers for the purpose of data analysis, but will destroy all copies of limited datasets no later than the completion of the project (31 May 2024).
- Pharmacy claims and dispensing data. Study team members at Sutter Health will obtain pharmacy claims and dispensing data via Surescripts, a third-party healthcare information technology organization, so that the study can track changes in opioid dispensing and refills.

The principal investigator, [name], has overall responsibility for the safeguarding of all data, and she will have primary responsibility for familiarizing all the project staff with this data safeguarding plan and procedures. She will follow up with project staff at periodic intervals to ensure that they are in compliance with these data safeguarding procedures.

The study site principal investigator, [name], will be responsible for ensuring that the Sutter Health EHR data is collected, stored, and shared in accordance with the procedures outlined above and approved by the RAND IRB.

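### The refill safety endpoint cannot occur in a patient discharged without an opioid and does not name new prescriptions, so Reports 1 and 2 can understate under-treatment and Report 3 leaves those patients out

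*Combined protocol and SAP*

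**What the plan says.** Section 9.4.3 lists two safety endpoints, 30-day emergency department visits and "Discharge opioid prescription refills". It gives no definition of a refill and no time window for it. The analysis is by reference: "The study statistician will regularly analyze these endpoints as outlined in section 8.2".

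Section 8.2 sets out three monthly ratio reports, which go to the half-yearly DSMB meetings:

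- Report 1 covers the whole arm: "Denominator: total number of INT1 patients meeting the inclusion criteria", and likewise for the other arms.
- Report 2 covers patients of surgeons who ever received an email. It is also compared with the Report 1 control ratio.
- Report 3 covers patients given a discharge opioid. In the nudge arms: "Denominator: total number of patients prescribed opioids at discharge and whose surgeon ever received an INT1 email". In control: "Denominator: total number of control patients prescribed opioids at discharge".

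On sources, section 8.2 states: "All safety assessments will be conducted using data collected from the Sutter Health electronic health record". Section 10.1.9.1 says that pharmacy claims and dispensing data will be obtained through Surescripts, "a third-party healthcare information technology organization, so that the study can track changes in opioid dispensing and refills". No section ties those data to the safety endpoint.

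Section 3 makes a reduction in the any-opioid share a secondary objective, with the endpoint "Share of discharges where any opioid was prescribed". Section 9.4.2 codes a discharge without an opioid as within guideline, so such discharges are in the study data.

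**The concern.** Apart from an emergency department visit, a refill is the only item in the DSMB reports that could show that a patient needed more pain relief than was supplied. Section 10.3 records that a patient pain survey was dropped. Section 2.3.1 cites unchanged refill rates in earlier studies as part of the case that risk is negligible. The refill row therefore carries weight.

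Patients who leave without an opioid because their surgeon changed practice are among those in whom under-treatment would matter most, and this endpoint cannot register them. A patient who returns and receives a fresh prescription is not clearly counted either. A lower refill ratio in a nudge arm could then be read as reassurance when part of it reflects only that fewer patients could have a refill.

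**Working it through.** **Inputs.** The documents give no opioid share, refill rate, threshold or sample size for this endpoint, so there is no stated figure to reproduce. All rates below are assumptions, shown over ranges. Let *q* be the share of eligible discharges with an opioid and *r* the refill rate among them.

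**Step 1: what the reports measure.** Report 1 = *q* × *r* + (1 − *q*) × 0 = *q* × *r*. Report 3 = *r*. Report 2 is the same kind of product for patients of emailed surgeons.

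**Step 2: pull from the any-opioid share alone.** With *r* equal in both arms, the Report 1 ratio (nudge/control) is *q*₁/*q*₀:

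| Control *q*₀ | no fall | 5-point fall | 10-point fall | 20-point fall |
|---|---|---|---|---|
| 0.90 | 1.00 | 0.94 | 0.89 | 0.78 |
| 0.80 | 1.00 | 0.94 | 0.88 | 0.75 |
| 0.60 | 1.00 | 0.92 | 0.83 | 0.67 |

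With *r* = 10%, the 0.80 to 0.70 case is 0.80 × 0.10 = 8.0% against 0.70 × 0.10 = 7.0%.

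**Step 3: the opposing pull.** Smaller quantities may raise *r*. The fall is cancelled when *r* rises by a factor *q*₀/*q*₁. Here 0.80/0.70 = 1.143, so *r* goes from 10% to 11.4%. If *r* rises by 30%, to 13%, Report 1 is 0.70 × 0.13 = 9.1% against 8.0%, a ratio of 1.14.

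**Step 4: what a broader event would show.** Assume that 3% of patients who would get no opioid in either arm later receive one. Assume also that a share *x* of the displaced 10 points (opioid under control, none under the nudge) return for one.

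- Control: 0.80 × 0.10 + 0.20 × 0.03 = 8.6%.
- Nudge: 0.70 × 0.10 + 0.20 × 0.03 + 0.10 × *x* = 7.6% + 0.10*x*.

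| *x* | refill-only ratio | any later opioid, nudge | ratio to 8.6% |
|---|---|---|---|
| 5% | 0.88 | 8.1% | 0.94 |
| 10% | 0.88 | 8.6% | 1.00 |
| 15% | 0.88 | 9.1% | 1.06 |
| 25% | 0.88 | 10.1% | 1.17 |

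The break-even is *x* = 10%, the assumed refill rate, because each displaced patient exchanges a 10% chance of a refill for a chance *x* of a new prescription. With a 5-point fall the refill ratio is 0.075/0.080 = 0.94. The broader ratio is then 0.0885/0.086 = 1.03 at *x* = 15% and 0.0935/0.086 = 1.09 at 25%. The refill row gives the same answer whatever *x* is.

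**Step 5: does Report 3 repair this?** At constant *r* its ratio is 1.00, so the structural zero is gone. But if the displaced patients would have refilled at rate *m*, the nudge-arm value becomes (0.80 × 0.10 − 0.10 × *m*)/0.70. That is 11.1%, 10.7%, 10.0% or 8.6% for *m* = 2%, 5%, 10% or 20%, against 10.0% in control. The report can move in either direction through selection alone.

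**Step 6: the data fields.** Section 8.1 lists opioid prescriptions before surgery, opioids in the 24 hours before discharge, the discharge order, and its refills. Neither 8.1 nor 8.2 lists a new opioid prescription after discharge.

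**The case against.** The strongest reply is that the nudges act on quantity. Under section 6.1.1 an email is triggered by prescriptions above the guideline amount. The nudges could succeed fully on the primary endpoint with *q* unchanged, and Report 1 would then move only with *r*, possibly upward. This stands. A reader might infer that the refill endpoint must fall as the nudges work, in proportion to their success. The documents do not support that: the pull runs only through the any-opioid share, and Step 3 shows how modest a rise in *r* offsets it.

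Second, section 8.2 requires numerators and denominators to be shown separately. The DSMB can therefore see a fall in prescribing by setting the Report 3 denominator against Report 2 in each nudge arm, and 3c against 1c in control. This also stands, and it weakens any claim that the DSMB would be misled. It does not supply the missing events, since seeing that fewer patients received an opioid does not show how many later needed one.

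Third, emergency department visits do not depend on a discharge opioid and remain a separate signal. That is correct. Thirty-day hospitalizations do not depend on one either. They sit under the safety objective in section 3 but are not among the items in 8.2 or 9.4.3.

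Fourth, section 10.1.6 leaves data elements to be defined at the DSMB's organizational meeting, and the charter is not available here. It might define a refill broadly. The protocol as written still points to the EHR and to refills of the discharge order.

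**Conclusion.** The point holds in a limited form. As worded, the endpoint cannot register further opioid need in no-opioid discharges and does not name new prescriptions. If the any-opioid share falls, Reports 1 and 2 carry a downward component and can understate under-treatment. Report 3 is a partial remedy: it excludes the no-opioid patients, conditions on something decided after randomization, and compares emailed surgeons with all control surgeons.

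On the assumed inputs the component is a ratio of 0.88 for a 10-point fall from 80%, and 0.67 to 0.94 across the falls of 5 to 20 points in Step 2. The net direction is not fixed, and the broader measure reverses the sign only if more than 10% of displaced patients return for an opioid.

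A reader might also infer that new prescriptions are deliberately excluded. The documents do not say so: the term is undefined, the field lists are not stated to be exhaustive, and the Surescripts data could capture such prescriptions.

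The *q* × *r* form assumes that Report 1 includes no-opioid discharges, as section 9.4.2 implies. Section 5.1 writes eligibility for oral opioid prescriptions. Read literally, that makes Report 1 opioid-only and Report 3's restriction redundant. The downward pull would then disappear, but the no-opioid patients would be absent from Report 1 altogether. The gap remains on either reading.

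**What to change.** In 8.2 and 9.4.3:

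- Add as a monitored event *any new or refilled opioid prescription written or dispensed within 30 days after discharge*, counted over all eligible discharges in each arm.
- Show it separately for patients with and without a discharge opioid, and with and without opioid prescriptions before surgery (already collected under 8.1), so that continuing users do not swamp the row.
- Keep refills as a sub-row.
- Use the Surescripts data of 10.1.9.1 together with the EHR, and amend the EHR-only sentence in 8.2.
- Reconcile 5.1 with 9.4.2 so that the Report 1 denominator is unambiguous.

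The split by discharge opioid is again post-randomization, so it is descriptive. The all-discharges row is the one to compare between arms.

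The cost is protocol wording and a change to the report program; the dispensing data are already planned. Dispensing data may arrive later than EHR data, and the row will include some prescriptions unrelated to surgery in all arms.
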